Principle Investigator

NCT06262191

December 18, 2024

Statistical Analysis Plan

Ankle joint kinematics and kinetics were calculated in OpenSim using the collected three-dimensional motion capture and the ground reaction forces. The joint kinematics and ground reaction forces were filtered using a low pass fourth order recursive Butterworth filter with a cut-off frequency of 6 Hz before being used to calculate joint kinetics. The ground reaction forces were collected using two force places associated with the instrumented treadmill (Bertec Corp, Columbus, USA) collected at 1200 Hz. The resultant joint kinetics were then further filtered using the same filtering parameters. Joint power was calculated as the product of the joint moment and joint angular velocity.

EMG was collected using wireless EMG sensors (Delsys Trigno, MA, USA). A sensor was placed on the soleus (SOL) muscle belly 2/3 of the distance between the medial condyle of the femur to the medial malleolus. We computed the linear envelope for each EMG signal by demeaning, bandpass filtering between 380 and 15 Hz (fourth-order Butterworth), and then low pass filtering the rectified signal with a cutoff of 7 Hz.

For EMG analysis, the integrated soleus muscle activity was computed during the last 50% of stance phase, and the integrated vastus lateralis EMG activity was quantified during the entire stance phase. To calculate the metabolic cost of transport, the standing baseline metabolic rate for each participant and each trial was subtracted from their walking metabolic rate to estimate the net metabolic rate of walking. Next, we normalized the net metabolic rate of walking by each participant's body mass and walking speed to calculate the metabolic cost of transport, averaged over the last two minutes of each condition. To quantify peak ankle push-off power, we identified the maximum ankle and hip power during the last 50% of the stance phase for each step.

To evaluate changes in our outcome measures, we used paired T-tests to test for differences in each outcome variable between the adjustable stiffness AFO and shod walking conditions. We tested for sphericity using Mauchly's test and used the Greenhouse-Geisser correction if data did not meet the sphericity assumption. Sidak adjusted p-values were used to reduce the chance of type I errors; the alpha level was set to .05. Partial eta squared was used to estimate effect size.

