Our long-term goal is to establish effective therapies that restore function and improve mobility to enable increased levels of habitual physical activity for improved quality of life and longitudinal health outcomes in individuals with CP. The primary goal of this study is to validate the benefits of, and customer need for, differential and adjustable stiffness AFO features.

Our first aim is to confirm that the differential and adjustable stiffness (DAS) AFO improves plantarflexor push-off power and range of motion compared to standard (physician prescribed) AFOs during walking in CP.

Our second aim is to confirm that the differential and adjustable stiffness (DAS) AFO improves plantarflexor muscle activity while maintaining improved posture compared to standard AFOs during walking in CP.

Our third aim is to validate the need and usability of real-time stiffness adjustment during play and school activities; obtain feedback from the children, their parents, and orthotists to design the MVP.

Lay Summary:

This study seeks to determine how an adjustable stiffness ankle braces affects walking performance and biomechanics in cerebral palsy.

Resources:

This study will take place in the Biomechatronics Lab led by PI Assoc. [name]. Post-docs, graduate student researchers and undergraduate student researchers will be assisting with data collection and processing.

Population & Recruitment

- Maximum number of participants to be enrolled in the study: 11
- Please check all the categories of participants that will be included in the research:

 Children (1-17 yrs old)- Complete Appendix A	 Adults
 Prisoners- Complete Appendix C	 Refugees
 Native Americans - See the Tribal Consultation Policy	 NAU Staff/Faculty
 Pregnant Woman/ Neonates – Complete Appendix B	 NAU Students
 Cognitively Impaired Subjects	 Other- Explain Below

Project Narrative for Prospective Research

- What are the inclusion and exclusion criteria for study participation?

Inclusion Criteria:

- Age between 8-45 years old, inclusive
- Diagnosis of cerebral palsy (CP)
- Gross motor functional classification score level I, II, or III
- Physician-prescribed AFOs of common design (i.e., rigid molded thermoplastic)

Exclusion Criteria:

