- Excessive knee flexion during walking caused by CP
- Ability to walk for 6 minutes on a treadmill
- At least 20° of passive plantar-flexion range of motion
- No concurrent treatment other than those assigned during the study
- No condition other than CP that would affect safe participation
- No surgery within 6 months of participation.

- Indicate age range, gender and ethnicity of your research population:

There will be no restriction on sex, gender, ethnicity, or race.

Age between 8-45 years old.

- Will there be any individuals working on the research project (consenting, collecting data, analyzing identifiable data) who are not affiliated with NAU? No Yes- Please complete **Appendix E: Multi-site Research** for each unique site if the site will not obtain their own IRB approval.

- Will any documents be translated into another language? No Yes- Please explain below
Explain: Click or tap here to enter text.

- Please select the methods that will be used to recruit individuals. **Provide copies of documents, as applicable.**

 Email	 Social Media
 Flyers	 Online Advertisements
 TV, Radio, Print	 Phone Calls
 In Person Presentations	 Screening of the Electronic Medical Record (EMR)
 Face to Face	 SONA
	 Other- Please explain below

Explain: We will use an email, phone, and face to face script for participant recruiting

- When will recruitment occur? Please provide time frame with dates if applicable: 1/1/2024-1/1/2025
- Please explain the recruitment process (who is recruiting, how and where will recruitment take place?): The PI, staff, and students assigned to the project.

Project Narrative for Prospective Research

- Will 1,000 or more NAU members (prospective, current, or former students, or faculty, staff, or alumni) be solicited/recruited (e.g., NAU Listservs, etc.) to be surveyed?

No Yes [See the Conducting University Surveys Policy.](#)

Informed Consent

1. Please indicate the informed consent process(es) and/or document(s) to be used in the study. Check all that apply. **Provide copies of documents, as applicable.**

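### The SAP's only stated contrast is with shod walking, so as written it does not test Aims 1 and 2 against the standard AFO, and nothing shows when that contrast was set

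*SAP*

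**What the plan says.** The protocol words both biomechanical aims as confirmatory. Aim 1 (Purpose): "Our first aim is to confirm that the differential and adjustable stiffness (DAS) AFO improves plantarflexor push-off power and range of motion". Aim 2 (same section): "Our second aim is to confirm that the differential and adjustable stiffness (DAS) AFO improves plantarflexor muscle activity while maintaining improved posture". Each sentence goes on to name the standard AFO as the comparator, which Aim 1 glosses as the one prescribed by the physician. The Overview repeats both aims.

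The Experimental Protocol for Aim 1 and 2 describes a final assessment with two walking conditions in block-randomized order: the participant's normal AFOs and the tuned DAS-AFO. The protocol has no analysis section and names no primary outcome. Its Outcome Measures list gives types of data that may be collected.

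The SAP holds the only analysis. It is in the past tense for processing ("Ankle joint kinematics and kinetics were calculated in OpenSim using the collected three-dimensional motion capture and the ground reaction forces") and for testing. Its final paragraph gives the contrast: "we used paired T-tests to test for differences in each outcome variable between the adjustable stiffness AFO and shod walking conditions". It then adds: "We tested for sphericity using Mauchly's test and used the Greenhouse-Geisser correction if data did not meet the sphericity assumption". Both documents carry the cover date "December 18, 2024". Neither cites an earlier analysis plan, a date of approval or a data lock.

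**The concern.** An analysis plan has to test the comparison that the aims state. Here the aims ask whether the new orthosis does better than the one the child already wears, and the SAP answers a different question: whether walking in the new orthosis differs from walking shod. A positive shod result could be reported as confirming Aim 1 or Aim 2 when the comparison with the standard AFO had not been made.

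The form of the SAP adds to this. It describes completed work, and there is no prospective analysis text to set beside it. A reader who sees the comparator change between protocol and SAP therefore cannot tell whether the change came before or after the data were processed by condition.

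**Working it through.** The plan gives no power calculation, effect size or number of comparisons, so there is no figure to reproduce. The check sets the passages side by side.

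**1. Conditions and contrast.**

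| Source | Conditions named |
|---|---|
| Protocol, Purpose and Overview (Aims 1 and 2) | DAS-AFO versus standard AFO |
| Protocol, procedure for Aims 1 and 2 | normal AFO; DAS-AFO |
| SAP, final paragraph | DAS-AFO versus shod |

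The aims and the procedure agree with each other. Eligibility also requires a prescribed AFO, so every participant can supply the comparator. The SAP is the odd one out: of the two conditions its contrast needs, the procedure includes one.

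**2. Can the shod contrast stand in for the aim?** For any one outcome, write D, S and H for the mean in the DAS-AFO, the standard AFO and shod walking. The aim concerns D − S. The SAP tests D − H. They are linked by

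D − S = (D − H) − (S − H).

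The term S − H is not estimated anywhere in the SAP, so the sign of D − H does not fix the sign of D − S. The error can run either way:

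- Push-off power. The protocol's Background argues that current AFOs interfere with push-off and often reduce ankle power. That implies S − H < 0, so D − S would exceed D − H. Aim 1 could be true while the shod test shows nothing.
- Posture. If the standard AFO improves posture over shoes alone (an assumption; the documents give no figure), then S − H > 0. The DAS-AFO could beat shod walking and still fall short of the standard AFO.

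**3. Coverage of the aim-named measures.**

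| Measure | Aim | Defined in SAP? | Stated contrast with standard AFO? |
|---|---|---|---|
| Push-off power | 1 | yes, maximum in the second half of stance | no |
| Range of motion | 1 | no; ankle kinematics are computed but no such outcome is named | no |
| Plantarflexor activity | 2 | yes, integrated soleus EMG | no |
| Posture | 2 | no | no |

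Two of the four measures are defined, and none of the four has a stated test against the aims' comparator.

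**4. Timing.** The SAP's wording says data had been collected and tests run. No other dated analysis text appears. The documents therefore do not show that the contrast was fixed beforehand.

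**The case against.** **The standard-AFO comparison may have been made but not written down.** Mauchly's test and the Greenhouse-Geisser correction point to a repeated-measures model. With k conditions there are k(k − 1)/2 variances of paired differences: one when k = 2, so sphericity cannot fail, and three when k = 3. The SAP's text makes sense only with at least three conditions, and the standard AFO is a natural third. It is also possible that *shod* was used loosely. This has force, and it would make the correction easy. But the SAP lists no conditions, does not define the term, and states only the shod contrast.

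**The timing evidence is weak.** This stands. A reader might infer from the cover date that the analysis was chosen late: 18 December 2024 is 14 days before the end of the recruitment window ("Please provide time frame with dates if applicable: 1/1/2024-1/1/2025"). The documents do not support that. The protocol bears the same bare date and is written in the future tense, although its window opened almost a year before, so the date does not show when either text was composed. The window is also a planned one, and actual enrolment and lock dates are not given. An earlier plan may exist elsewhere.

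**The SAP's other additions are not departures.** This also stands. A reader might count vastus lateralis EMG, hip power and the stance-phase windows as unannounced. The Outcome Measures list includes electromyography without restriction on muscle, and motion capture and ground reaction forces, from which hip power derives. Metabolic cost of transport is listed by name, so post hoc would be the wrong label for it. Specifying windows is a SAP's job. None of these, however, is a measure that Aim 1 or 2 names.

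**This is a small study and *confirm* is loose wording.** With at most 11 participants and no power claim, that may be so. It bears on how strongly results are worded, not on which comparison answers the aims.

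**Conclusion.** The point holds, as an error of comparator: wrong as written. The SAP's stated contrast cannot answer Aim 1 or Aim 2. Its size is a count: none of the four aim-named measures has a stated test against the standard AFO, and two of the four have no defined outcome. This rests only on the text of the two documents. It would fall away if the sponsor showed that the standard-AFO contrast was in fact specified.

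The timing part is smaller. The documents do not show that the contrast was set before processing. It does not follow that it was chosen after results were seen. Nor can an inflated false-positive rate be derived, since any such figure would need an assumed number of alternative analyses and assumed correlations between them, and the documents give neither.

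**What to change.** In the SAP's final paragraph:

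1. Make the aim-testing contrast DAS-AFO versus the participant's standard AFO. Apply it to peak ankle push-off power and ankle range of motion for Aim 1, and to soleus activity and posture for Aim 2. Define the range-of-motion and posture measures, which the SAP now lacks.
2. Report any shod contrast, hip power, vastus lateralis EMG and metabolic cost of transport as secondary or exploratory, and do not cite them in support of *confirm*. If shod walking was recorded, say so and list every condition analysed.
3. Add a sentence stating when the analysis was fixed relative to the first processing of data by condition, citing any earlier dated plan. If there is none, disclose that as a limitation.

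Leave the wording of Aims 1 and 2 as it is. Rewriting aims when data may already have been seen would blur the record.

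The cost is SAP text and a re-run of paired comparisons if the standard-AFO contrast has not been computed. No new participants or visits are needed, provided the normal-AFO walk was recorded as the protocol describes. The downside is a less favourable claim for some outcomes.

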Why do we need quickly adjustable AFO stiffness? Improving mobility in the community requires adjustable ankle stiffness. Ankle joint stiffness varies considerably across different speeds and terrains, which suggests the same for optimal AFO stiffness. Unfortunately, commonly prescribed AFOs are unable to easily or quickly vary the joint stiffness; most are not able to vary stiffness at all. The result, at best, is a single AFO stiffness that is only optimized for ambulating in a single condition at a single speed. AFOs are typically too stiff for slower speeds, often even prevent children from getting off the ground, and yet also unsuitable for stair climbing, ramp ascent or descent, and running. Research has demonstrated that individually tuned stiffness is critical for maximizing improvements in walking performance in CP [19]. There is a need to create an AFO where children can change the stiffness themselves “on the fly.”

Why do we need differential AFO stiffness? There may be long-term danger of locking the ankle and preventing plantarflexion during walking [20]. AFOs typically resist ankle plantar flexion by the same amount that they resist ankle dorsiflexion, resulting in a dramatic reduction in active neuromuscular engagement of the plantar flexor muscles, reduced range of motion, and minimal ankle push-off power [20]. One paper demonstrated that spring like differential stiffness preserves ankle power and work in CP, whereas a rigid configuration did not [18]. There is a need to create an AFO that allows users to maintain some ability to plantarflex at the ankle.

Project Narrative for Prospective Research

Why do we need a modular design? A design that allows the calf cuffs and footplates to be customized and interchanged based on changing needs or growth has several benefits. First, it reduces waste for expensive and hard to recycle composite materials (e.g., carbon fiber). Second, it reduces the need for custom molding sessions. Third, it may allow us to reduce fabrication costs by benefiting from economies of scale when manufacturing common sizes and form factors. There is a need to create an AFO that grows with the child and adapts to their needs.

Purpose:

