Overview: We have developed a differential and adjustable stiffness AFO (DAS-AFO): Differential stiffnesses allows for customizing the stiffness in the plantarflexor and dorsal directions separately to maximize neuromuscular engagement and positive biological ankle power during push-off; A “real-time” stiffness adjusting slider allows for rapid and easy adjustment for different ambulatory conditions (e.g., walking, stairs, running). The primary goal of this study is to validate the benefits of, and need for, differential and adjustable stiffness AFO features. Our first aim is to confirm that the differential and adjustable stiffness AFO improves plantarflexor push-off power and range of motion compared to standard (physician prescribed) AFOs during walking in cerebral palsy (CP). Our second aim is to confirm that the differential and adjustable stiffness AFO improves plantarflexor muscle activity while maintaining improved posture compared to standard AFOs during walking in CP. Our third aim is to validate the need and usability for real-time stiffness adjustment during play and school activities; obtain feedback from the children and their parents.

Experimental Protocol for Aim 1 and 2: Participants will complete two 30-minute practice sessions, and a final assessment. On the final assessment, participants will walk on an instrumented treadmill for 6 minutes with their normal AFOs and with the DAS-AFO tuned to provide just enough dorsiflexor assistance to address drop foot (if present). Testing order will be block randomized. Treadmill speed will be set to each participant’s preference, as will the stance phase plantarflexor stiffness for the DAS-AFO.

Experimental Protocol for Aim 3: Participants will complete a series of play and school activities using the DAS-AFO and their normal AFOs; order will be block randomized. During the DAS-AFO condition, participants will be instructed to adjust stiffness using the simple slider as desired. Activities will include a series of floor-seated, chair-seated, standing, walking, and running (if applicable) tasks to capture the breadth of possible movements encountered during a typical school day. We will use video recording to observe and characterize interactions. These sessions will be followed by dedicated discussion time and validated product evaluation/usability questionnaires.

Outcome Measures: The following experimental data may be collected under each experimental protocol:

- Electromyography

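### The SAP tests the adjustable stiffness AFO against shod walking, but Aims 1 and 2 and the treadmill protocol compare it with the physician-prescribed AFO, so neither aim is tested

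*SAP*

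**What the plan says.** The comparator for both walking aims is fixed in the protocol's Purpose section and repeated in the Overview of the research procedures. Aim 1 is to confirm that the device "improves plantarflexor push-off power and range of motion compared to standard (physician prescribed) AFOs during walking in CP". Aim 2 is to confirm that it "improves plantarflexor muscle activity while maintaining improved posture compared to standard AFOs during walking in CP".

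The section Experimental Protocol for Aim 1 and 2 matches this. Its account of the last visit reads: "participants will walk on an instrumented treadmill for 6 minutes with their normal AFOs and with the DAS-AFO tuned to provide" (the sentence goes on to the drop-foot setting). The order of the walks is block randomized. A physician-prescribed AFO is an inclusion criterion, so every eligible participant brings the comparator. No walk in shoes alone is described.

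The SAP's final paragraph states a different contrast: "we used paired T-tests to test for differences in each outcome variable between the adjustable stiffness AFO and shod walking conditions". It then says the analysts tested sphericity with Mauchly's test and "used the Greenhouse-Geisser correction if data did not meet the sphericity assumption", with Sidak-adjusted p-values, alpha .05 and partial eta squared. It names no ANOVA, no factor and no list of conditions. The words standard, normal and prescribed AFO do not occur in the SAP.

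**The concern.** The comparator in the aims is missing from the analysis, and the comparator in the analysis is missing from the protocol. Neither document defines shod; it is read here as shoes without an AFO.

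The two comparators are not interchangeable. In the section on why differential stiffness is needed, the protocol says typical AFOs lower plantarflexor engagement and lead to "reduced range of motion, and minimal ankle push-off power". Those are Aim 1 and Aim 2 outcomes, so the protocol itself expects shod walking and standard-AFO walking to differ on them. A DAS-AFO could fall below shod walking and still be clearly better than the standard AFO. The SAP would then report a decrement in a study whose first aim had been met. A finding of no difference from shod walking would likewise leave the aim unanswered.

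**Working it through.** **The texts side by side**

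| Source | Conditions compared |
|---|---|
| Protocol, Purpose, Aim 1 | DAS-AFO vs standard (prescribed) AFO |
| Protocol, Purpose, Aim 2 | DAS-AFO vs standard AFO |
| Protocol, Experimental Protocol for Aim 1 and 2 | Walks in the normal AFO and the DAS-AFO |
| SAP, final paragraph | Adjustable stiffness AFO vs shod |

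The documents give no power, effect size or SD, so the plan has no figure to reproduce.

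**What the sphericity wording implies**

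For k within-subject conditions, Mauchly's test has k(k-1)/2 - 1 degrees of freedom, and the lower bound of the Greenhouse-Geisser epsilon is 1/(k-1).

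- k = 2: df = 1 - 1 = 0 and lower bound = 1. The step does nothing. There is one pairwise contrast, so Sidak leaves alpha at 0.05 unless the family is the set of outcomes.
- k = 3: df = 3 - 1 = 2 and lower bound = 0.5. There are three pairs, and the Sidak level per pair is 1 - 0.95^(1/3) = 0.0170.

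The wording therefore hints at three or more conditions, but no such model and no standard-AFO contrast is written.

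**What the SAP contrast leaves open**

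Write D for DAS-AFO, S for standard AFO and N for shod. Then

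D - S = (D - N) + (N - S).

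The SAP estimates D - N only. The values below are assumptions, in points of the shod value, with D - N held at -10:

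| Assumed S - N | N - S | Aim 1 contrast D - S |
|---|---|---|
| 0 | 0 | -10 |
| -10 | 10 | 0 |
| -20 | 20 | +10 |
| -30 | 30 | +20 |
| -40 | 40 | +30 |

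One SAP result fits harm, no difference or benefit. Taken as an answer to Aim 1, it is off by exactly N - S.

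**How often the two tests would point in opposite directions (illustration)**

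Assumptions: all 11 participants complete (the protocol states "Maximum number of participants to be enrolled in the study: 11"); two-sided unadjusted 0.05; true D - N = -10 and true D - S = +20; the same SD of paired differences for both contrasts. The critical t on 10 df is 2.228, and the noncentrality is |difference| × √11 / SD.

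| Assumed SD | Noncentrality, D - N | P(SAP test significantly negative) | Noncentrality, D - S | P(Aim 1 contrast significantly positive) |
|---|---|---|---|---|
| 10 | 3.317 | 0.848 | 6.633 | >0.99 |
| 20 | 1.658 | 0.323 | 3.317 | 0.848 |
| 30 | 1.106 | 0.169 | 2.211 | 0.515 |

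**The case against.** The strongest reply is that the text may misdescribe what was done. The protocol has two conditions and the SAP a two-condition paired test, so shod could be a wrong label for the normal-AFO walk. Alternatively, the sphericity wording could be left over from a three-condition analysis that contained the needed contrast. The documents settle neither reading. What stands is a limit on the claim: it is certain that the written contrast does not match the aims, but not that the wrong contrast was computed. Under either reading the paragraph still has to be corrected.

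The illustration is also open to challenge. Every effect and SD in it is assumed, and no statement in the protocol puts the DAS-AFO 10 points below shod; its background cites evidence that spring-like differential stiffness preserves ankle power. In the grid, harm arises only if the standard AFO equals shod, which the protocol does not expect. The probabilities ignore the Sidak adjustment. A negative result would also be a correct answer to the contrast the SAP names, and misleading only if read as the answer to Aim 1. All of this is fair. The probabilities show what could happen, and the finding does not rest on them.

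Finally, replacing partial eta squared is a preference, since it can be computed with two conditions. That is conceded.

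**Conclusion.** The concern holds and must be fixed. As written, no test in the SAP addresses Aim 1 or Aim 2, and the comparator it names is not a protocol condition. This follows from the two documents alone and needs no assumed number.

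The size of the discrepancy for any outcome is the shod-minus-standard difference, which the documents do not give. Over an assumed range of 0 to 40 points, the same SAP result of -10 corresponds to an Aim 1 effect of -10 to +30. In the assumed case of a true 20-point benefit over the standard AFO, the SAP's test would be significantly negative with probability 0.17 to 0.85 as the SD falls from 30 to 10 points. These figures assume that shod means shoes without an AFO, and the probabilities also assume 11 complete pairs and unadjusted two-sided tests.

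**What to change.** Rewrite the SAP's test paragraph so that the paired DAS-AFO minus physician-prescribed AFO difference is the test for every Aim 1 and Aim 2 outcome and the basis for the conclusions on those aims. Then:

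- **If only two conditions were run:** drop Mauchly and Greenhouse-Geisser, and apply Sidak across a listed set of outcomes. Reporting the mean paired difference with its 95% CI and a standardised paired difference would be clearer than partial eta squared.
- **If three were run:** name the repeated-measures model and its Sidak-adjusted pairwise contrasts, including DAS-AFO versus standard AFO.
- **Shod:** if shod trials took place, define the term, document the trials and their actual order in the protocol, and report DAS-AFO versus shod as secondary. Otherwise remove shod from the SAP; this also covers the case of a wrong label.
- **Dating:** date the change and state whether data had already been examined. The SAP is in the past tense and dated December 18, 2024, two weeks before the stated end of recruitment (1/1/2025).

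The cost is one SAP paragraph and, if shod trials were run, a short protocol clarification. If the shod contrast really was the one computed, the analyses must also be re-run. No new walking condition is needed, because the prescribed-AFO walk is already scheduled. One check is needed: the protocol's Outcome Measures section says only that "The following experimental data may be collected under each experimental protocol", so confirm that each Aim 1 and Aim 2 outcome was recorded in that walk. The SAP also defines no range-of-motion or posture variable, so those two need a definition before the corrected contrast can be applied to them.

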3. For each of the platforms checked above (both hard copy and electronic information), discuss the type of data to be stored in each platform (including if the data is identifiable), who may have access to the platform, and how long the information will be stored: [Click or tap here to enter text](#).

De-identifiable experimental data and an excel file with participant demographic information (i.e., walking ability, GMFCS Score, height, weight, age) may be stored on our lab's Google Drive account;

Project Narrative for Prospective Research

this information will be stored indefinitely. Everyone in the Biomechatronics Lab will have access to these data. Identifiable information (e.g., consent form) will be stored in hard copy form in the PI's locked drawer in his locked office; this info will be stored for 5 years after study completion.

4. Discuss how, when and why subjects/data may be removed from the study. If abrupt withdrawal is necessary, discuss how subjects will be withdrawn so that they are not put at increased risk. Discuss what happens if a subject is withdrawn from one part of the study but asked to continue with other parts, such as ongoing follow-up: [Click or tap here to enter text](#).

Withdrawal Circumstances:

Participants will be withdrawn if they are later identified as not meeting the inclusion criteria (e.g., identified as eligible in error), if they miss more than 2-3 research visits in a given experiment, or if they decide to stop participating in the study.

Withdrawal Procedures:

If a participant consents to the study but elects to stop participating after data collection has started, any data that was collected will be retained unless the participant asks otherwise.

Participants must alert the study team in writing of their request to be withdrawn from the study.

Termination Procedures:

Data collected and completed up to the point of withdrawal or termination will still be included in the study unless the participant asks otherwise.

5. Describe steps, if any, to protect the privacy of the subjects throughout their participation in the Human Research (e.g. during the recruitment process, consent process, and/or research procedures): [Click or tap here to enter text](#).

Study team members are trained on appropriate data use and storage, and every reasonable effort is made to minimize risk associated with loss of privacy and confidentiality.

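### Walk order is block randomised but the paired t-tests carry no period term, so an order effect would cost precision near balance and shift the estimate if the orders are unequal

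*SAP*

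**What the plan says.** The protocol (Data Collection Procedures, item 2, Experimental Protocol for Aim 1 and 2) says that at the final assessment "participants will walk on an instrumented treadmill for 6 minutes with their normal AFOs and with the DAS-AFO", and then: "Testing order will be block randomized". It gives neither the block size nor the planned number in each order. Population & Recruitment sets the size: "Maximum number of participants to be enrolled in the study: 11".

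The final paragraph of the SAP says "we used paired T-tests to test for differences in each outcome variable", and the contrast it names is "between the adjustable stiffness AFO and shod walking conditions". It adds: "We tested for sphericity using Mauchly's test and used the Greenhouse-Geisser correction if data did not meet the sphericity assumption". P-values are Sidak-adjusted and "the alpha level was set to .05".

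Neither document mentions a period, order or sequence term, a check for order effects, or a sensitivity analysis by order.

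**The concern.** Two walks per person at one assessment, in randomised order, form a two-period, two-sequence crossover. Randomising the order protects the comparison on average, but a paired t-test makes no use of the order that was assigned. If people tire, or warm up, between the first and second walk, those who wore the DAS-AFO second have their difference moved one way, and those who wore it first have it moved the other way. The paired test counts that spread as random error. If more people had one order than the other, the movements do not cancel and the remainder is reported as a device effect.

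Push-off power, soleus EMG and metabolic cost could each respond to fatigue or warm-up. With at most 11 people there is little precision to spare for Aims 1 and 2.

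**Working it through.** **No plan figure to reproduce.** The documents give no effect size, SD, power or sample-size calculation.

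**Inputs from the documents.** Two order-randomised conditions (protocol, Aim 1 and 2); paired t-test per outcome and alpha 0.05 (SAP); at most 11 people (protocol).

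**Assumptions.** Two-sided testing (the SAP does not say). A level of 0.05 per test, before any Sidak adjustment, because the SAP does not state the number of tests. P = 0, 0.25, 0.5 and 1. Splits 5:5, 6:5, 7:4 and 8:3.

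**Model.** In units of the SD of the paired difference, d = τ + sP + e. Here d is the DAS-AFO value minus the comparator value, τ is the device effect, s is +1 if the DAS-AFO was walked second and −1 if first, and e has SD 1. n1 and n2 are the numbers with s = +1 and s = −1, and n = n1 + n2.

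**Paired t-test (n−1 df).**
- Shift of the estimate: P(n1−n2)/n. This is 0 at 5:5, P/11 = 0.09P at 6:5, 3P/11 = 0.27P at 7:4 and 5P/11 = 0.45P at 8:3.
- Expected variance of the differences: 1 + P²·4n1n2/[n(n−1)]. At 6:5 the factor is 120/110 = 1.091, so the SD is √(1+1.091×0.0625) = 1.03 at P=0.25, √(1+1.091×0.25) = 1.13 at P=0.5 and √2.091 = 1.45 at P=1.

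**Period-adjusted analysis (n−2 df).** The estimate is the average of the two order-specific mean differences. Its standard error is √[s²(1/n1+1/n2)/4], with s² pooled within orders. P cancels from both.

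**Simulated results at 6:5** (at least 200,000 trials per setting):

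| P | Mean 95% CI width, paired | Mean 95% CI width, adjusted | Type I error, paired |
|---|---|---|---|
| 0 | 1.31 | 1.33 | 5.0% |
| 0.25 | 1.355 | 1.333 | 4.4% |
| 0.5 | 1.48 | 1.33 | 3.1% |
| 1 | 1.91 | 1.33 | 0.9% |

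The adjusted test holds about 5% throughout. The two widths break even near P = 0.2.

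**Power at 6:5, P=1, for a device effect of 0.8.** The paired test has 43% if the extra person is in the order that pushes the estimate towards the device effect, and about 25% if in the other order. The adjusted test has 65% either way.

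**Other splits.** At 5:5 there is no shift, but the type I error of the paired test still falls to 4.4%, 3.0% and 0.6% at P = 0.25, 0.5 and 1. At 8:3 the shift outweighs the larger SD, and type I error is 5.7%, 7.4% and 10.1%. At 7:4, P=0.5 and effect 0.8, the paired test shows 72% power against 62% adjusted, but only because the shift happens to favour the device.

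**Cost of adjusting when P=0.** The ratio of interval widths is roughly [t(n−2)/t(n−1)] × √[(1/n1+1/n2)/4] / √(1/n). With 11 people the t ratio is 2.262/2.228 = 1.015 and √(1/11) = 0.3015. At 6:5: 1.015 × 0.3028/0.3015 = 1.02. At 7:4: 1.015 × 0.3134/0.3015 = 1.055 (simulated widths 1.31 to 1.38, about 5%). At 8:3: 1.015 × 0.3385/0.3015 = 1.14.

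**The case against.** The strongest objection is that the SAP does not test the randomised comparison. Its contrast is with shod walking, whereas the protocol randomises the order of normal AFOs and DAS-AFO and lists no shod walk. The sphericity wording also suggests three or more conditions. This stands, and it governs how the fix is written. A two-sequence analysis suits only a contrast of two order-randomised walks, and if shod walking always held the same position, no order term can separate its effect from that position.

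Second, P is unknown and may be small. Participants have two 30-minute practice sessions and walk at their preferred speed. Metabolic cost is net of a standing baseline for each trial and averaged over the last two minutes. These features may reduce an order effect, particularly learning, but do not rule out fatigue within the visit. Below about P = 0.2 at 6:5, adjusting slightly widens the interval.

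Third, adjusting is not always cheap: the cost grows with imbalance, which is also where bias matters most. This stands too.

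Stronger readings that the documents do not support:
- *The test gives too many false positives.* Near balance it gives fewer. Among the splits tried, type I error exceeded 5% only at 8:3, and nothing shows that such a split occurred.
- *The orders cannot balance.* Eleven is a maximum; 10 completers can split 5:5.
- *The protocol promises that single walks will be analysed.* The statement "Data collected and completed up to the point of withdrawal or termination will still be included in the study" sits under Privacy and Confidentiality (item 4) and concerns data retention. It does not define an analysis set, and both walks belong to one assessment.
- *Aim 3 has the same fault.* Its order is also block randomised, but the SAP sets out no separate Aim 3 analysis, and the protocol does not say that the questionnaires are scored per condition.

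**Conclusion.** The concern holds in a limited form: the design randomises order and the analysis ignores it. Near balance the consequence is lost precision, negligible at P=0.25 but about 11% more interval width at P=0.5 (1.48/1.33) and 43% more at P=1 (1.91/1.33). Bias is a smaller matter at 6:5 (0.045 SD at P=0.5, from 0.5/11) and becomes material only with splits such as 7:4 or worse.

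These sizes rest on assumed values of P, on an order effect that adds equally in both orders, and on a contrast whose two walks were order-randomised. The documents confirm that last condition for normal AFO against DAS-AFO, but not for the shod contrast that the SAP names. The case for changing the analysis is one of asymmetry: a small premium near balance if there is no order effect, and a substantial loss if there is a large one.

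**What to change.** 1. Reconcile the SAP's shod contrast with the protocol's comparison of normal AFOs and DAS-AFO. State which conditions were walked and which had a randomised position.
2. Report the number of participants in each order.
3. For a two-condition contrast with randomised order, make the period-adjusted crossover analysis the main one: the average of the two order-specific mean differences, pooled within-order variance, n−2 df (9 df for 11 people). A mixed model with condition and period as fixed effects and participant as random is an alternative. Keep the paired t-test as a sensitivity analysis.
4. If more than two conditions were walked in randomised order, include walk position as a factor in the repeated-measures model.
5. If shod walking held a fixed position, state as a limitation that its contrast cannot be separated from position.

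The change needs no new data, only the recorded order. Once step 1 is settled the SAP wording is short. The statistical cost is one degree of freedom plus the loss from imbalance: with no order effect, intervals about 2% wider at 5:5 or 6:5, 5% at 7:4 and 14% at 8:3.
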